10. EFFICACY ANALYSES

All efficacy analyses will be performed using the ITT population. In addition, analyses of the primary efficacy endpoints will be performed using the PP population as a sensitivity analysis. All efficacy analyses and summaries will be based on assessments in the study eye for each subject.

The data for subjects who are rescued at any time after the first dose of study drug and before the efficacy assessments at POD15 will be handled as described in [Sections 6.4.2](#) and [6.4.3.1](#). The data for subjects who prematurely discontinue the study without taking any rescue medications will be handled as described in [Section 6.4.3.1](#).

The Analysis Visits (PODs 4, 8 and 15) defined in [Section 6.3.5](#) will be employed in the efficacy analyses.

Baseline values for the efficacy endpoints are defined as the assessment values obtained at POD1 pre-dose.

All efficacy data will be presented in listings.

10.1 Analyses of Primary Efficacy Endpoints

10.1.1 Primary Efficacy Endpoints

The primary efficacy endpoints are:

- The proportion of subjects with ACC count = 0 (ACC grade = 0) at POD8, maintained through POD15
- The proportion of subjects with Ocular Pain grade = 0 at POD4, maintained through POD15

The ACC count will be graded as shown below:

Grade	0	1	2	3	4
ACC Count	0 cell	1-5 cells	6-15 cells	16-30 cells	> 30 cells

The subject-rated Ocular Pain will be graded as follow:

Grade	Description
0	None: No pain.
1	Minimal: Presence of minimal throbbing or aching pain (expected following cataract surgery).
2	Mild: Presence of mild throbbing or aching pain, easily tolerated.
3	Moderate: Presence of moderate throbbing or aching pain leading to the desire to use an analgesic.
4	Severe: Presence of severe throbbing or aching pain that is not tolerable

10.1.2 Primary Analysis

The Pearson's Chi-square test will be used to test the null hypothesis that there is no difference between treatment groups for the primary efficacy endpoints:

1. The proportion of subjects with ACC count = 0 (ACC grade = 0) at POD8, maintained through POD15
2. The proportion of subjects with Ocular Pain grade = 0 at POD4, maintained through POD15

Since the treatment comparisons of the primary efficacy endpoints are in sequential order, the fixed-sequence hierarchical testing approach will be used to adjust for multiple comparisons. The primary analysis will first compare the proportion of subjects with ACC count = 0 (ACC grade = 0) at POD8, maintained through POD15, between APP13007 and placebo. If the test is statistically significant at the 2-sided $\alpha = 0.05$ level in favor of APP13007, the comparison of the

proportion of subjects with Ocular Pain grade = 0 at POD4, maintained through POD15, between APP13007 and placebo will be tested at the two-sided $\alpha = 0.05$ level.

Under the hierarchical testing scheme, once the two-sided p-value exceeds 0.05, the endpoint further down in the sequence will not be claimed for statistical significance.

The tabulated summary of the two endpoints will include the Responder (Response = Yes) and Non-responder (Response = No) for ACC count = 0 (ACC grade = 0) at POD8, maintained through POD15, or for Ocular Pain grade = 0 at POD4, maintained through POD15, and the 95% confidence interval (CI) for Responder. The treatment difference of the Responder rates with the associated 95% CI will be presented. The Response will be further categorized as:

Yes (Responder):

- Yes – Without imputed data
- Yes – With imputed data

No (Non-responder):

- No – With Rescue Medication Use
- No – Without Rescue Medication Use
- No – With imputed data

10.1.3 Sensitivity Analyses

Sensitivity analyses will be performed to confirm the robustness of the primary efficacy analysis results:

1. Analysis of the primary endpoints will be performed using the PP population.
2. “Completed-Case” analysis of the primary endpoints will be performed using the subgroup of Completers based on the ITT population. Completers are defined as the subjects who complete the study and have the data for the ACC count and ocular pain grade assessments at all visits up to POD15.
3. “Observed-Case” analysis of the primary endpoints will be performed using the ITT population and the observed data for subjects who miss one of the assessments used to determine the primary endpoints without taking rescue medication. The subjects with missing data will be considered as treatment failures (Non-responders).
4. “Worst-Case in the Analysis Window” analysis of the primary endpoints will be performed using the ITT population and using the worst Response at PODs 4, 8 and 15 when multiple efficacy assessments fall within the same analysis window for each Analysis Visit.
5. If more than 5% of data are missing for determining the primary efficacy endpoints in any treatment group, a tipping point analysis will be performed when the statistical significance of a treatment difference between two groups has been claimed for each of the two primary

endpoints. Missing data for subjects who take a rescue medication will not be considered as 'missing' since the subjects will have been assigned as treatment failures (Non-responders).

The tipping point analysis of the primary endpoints will be performed using the ITT population to determine the number of subjects with imputed data in the placebo group whose response status has to be changed from Non-Responder to Responder in order to make the treatment difference between the two treatment groups no longer statistically significant.

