10.6 PROCEDURE FOR ACCOUNTING FOR MISSING, UNUSED, OR SPURIOUS DATA

If more than 5% of data points are missing at POD15 in any treatment group, a tipping point analysis will be performed to assess the sensitivity of the primary efficacy results to the distribution of the allocation of treatment success and failure to the missing data points. Other missing data imputations will be detailed in the SAP.

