6.4.3 Handling Dropouts or Missing Data

6.4.3.1 Imputation of Missing Efficacy Data

The missing data handling rule for the study eye will be applied for the efficacy endpoints.

Missing data from subjects who discontinue the study before POD15 assessments without taking rescue medication:

For subjects who prematurely discontinue the study without taking rescue medication, the LOCF approach will be used to impute the missing data. The last observation will be the last assessment value after the first dose of study drug and up to two days following the last dose of study drug.

Missing data from subjects who discontinue the study before POD15 assessments and take rescue medication before POD15 assessments:

For both categorical and continuous secondary efficacy endpoints of ACC grade, ocular pain grade and ACF grade, subjects who take rescue medication before POD15 assessments and prematurely discontinue the study, the LOCF approach will be used to impute the missing data. The last observation will be the last assessment value after the first dose of study drug and prior to starting rescue medication.

Intermittent missing data:

The likelihood of having intermittent missing data is low. For subjects with intermittent missing data for efficacy endpoints, the LOCF approach will be applied to impute the missing data, i.e., using the data collected from the most recent prior visit after the first dose of study drug.

If no data can be carried forward (i.e., missing assessments at POD 4 visit or no available post-baseline assessments), missing data will be treated as missing for the continuous endpoints and will be considered as 'Non-responder' for the categorical endpoints.

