10.1.4 Additional Analysis

The primary efficacy endpoints will be analyzed using the data collected up to POD15. The rescued subjects will not be considered as treatment failures (Non-responders) for this analysis. All subjects' data collected up to POD15, including the data from subjects who take rescue medication, will be used to analyze the primary efficacy endpoints. Only observed data will be included to derive the primary efficacy endpoints. For the primary endpoint of ACC grade, subjects who miss one of POD 8 and POD15 assessments will be considered as treatment failures (Non-responders). For the primary endpoint of ocular pain grade, subjects who miss one of PODs 4, 8 and 15 assessments will be considered as treatment failures (Non-responders). The Pearson's Chi-square test will be used to test the treatment difference.

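### The tipping-point analysis changes only placebo Non-responders and never questions imputed APP13007 Responders, so it can report no tipping point where a two-way allocation loses significance

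*SAP*

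**What the plan says.** SAP section 10.1.3, item 5, sets the trigger: "If more than 5% of data are missing for determining the primary efficacy endpoints in any treatment group". The analysis is run once significance has been claimed for the primary endpoints. Rescued subjects do not count as missing, because they are already failures. The analysis is then defined in one direction and one arm only: "to determine the number of subjects with imputed data in the placebo group whose response status has to be changed from Non-Responder to Responder", until the difference is no longer significant.

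Imputed outcomes can arise in either arm. SAP section 6.4.3.1 states, without distinguishing treatment groups: "For subjects who prematurely discontinue the study without taking rescue medication, the LOCF approach will be used to impute the missing data". SAP section 10.1.2 expects some of these to be successes, since it plans a response category "Yes – With imputed data".

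Protocol section 10.6 describes the purpose of the analysis more broadly. It is to "assess the sensitivity of the primary efficacy results to the distribution of the allocation of treatment success and failure to the missing data points", with no restriction to placebo. Protocol section 10.3.2.1 leaves the details of the sensitivity analyses to the SAP.

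**The concern.** A tipping-point analysis should show how unfavourable the unseen outcomes would have to be before the conclusion fails. Two kinds of imputed outcome favour APP13007: carried-forward successes on APP13007 and carried-forward failures on placebo. Item 5 tests only the second kind.

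The trigger can be met by APP13007 dropout alone. If few placebo subjects are then imputed Non-responders, item 5 has little to change and leaves alone the arm whose missing data started it. If the placebo changes run out before p exceeds 0.05, the report will say that no tipping point was found, although another allocation of the same missing outcomes would lose significance. A reader would take that as stronger evidence of robustness than it is.

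**Working it through.** **1. Does another planned analysis close the gap?**

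| Analysis (SAP) | Imputed APP13007 Responders | Imputed placebo Non-responders |
|---|---|---|
| 10.1.3 item 1, Per-Protocol | not reallocated | not reallocated |
| 10.1.3 item 2, Completed-Case | not reallocated | not reallocated |
| 10.1.3 item 3, Observed-Case | become failures | stay failures |
| 10.1.3 item 4, Worst-Case in window | not reallocated | not reallocated |
| 10.1.3 item 5, tipping point | stay successes | become successes |
| 10.1.4, Additional Analysis | become failures | stay failures |

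No row moves both groups against APP13007. Observed-Case and 10.1.4 also turn imputed placebo Responders into failures, which partly offsets the change on APP13007.

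**2. The plan's own figures.** Inputs from Protocol section 10.4 and SAP section 4: cell-count (ACC) endpoint 26% v 12%, pain 57% v 38%, two-sided 5%, 175 per arm, 5% dropout.

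Power = Φ{[|p₁−p₂|√n − 1.96√(2p̄(1−p̄))] / √(p₁(1−p₁)+p₂(1−p₂))}

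- ACC: (0.14 × 13.229 − 1.96 × 0.5548) / 0.5459 = 1.40, power 91.9% (stated 92%).
- Pain: (0.19 × 13.229 − 1.96 × 0.7062) / 0.6933 = 1.63, power 94.8% (stated 95%).
- 175 / 0.95 = 184.2, so 185 per arm.

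The stated figures reproduce.

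**3. The test.** Pearson chi-square without continuity correction. With 185 per arm and a v b responders, it reduces to

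χ² = 370(a−b)² / [(a+b)(370−a−b)], 1 degree of freedom.

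At the design rates:

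- ACC: 0.26 × 185 ≈ 48 and 0.12 × 185 ≈ 22. χ² = 370 × 26² / (70 × 300) = 11.91, p = 0.0006.
- Pain: 0.57 × 185 ≈ 105 and 0.38 × 185 ≈ 70, p = 0.0003.

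**4. When item 5 starts.** 5% of 185 is 9.25, so at least 10 subjects must be missing in one arm.

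**5. Comparing the rules.** Assumptions not in the documents: observed rates equal the design rates, k subjects are missing in each arm, and their imputed responses split at that arm's design rate (rounded).

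Example, ACC, k = 10: 3 imputed Responders on APP13007 (0.26 × 10); on placebo, 1 imputed Responder (0.12 × 10) and 9 Non-responders.

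- Item 5, all 9 changed: 48 v 31, χ² = 370 × 17² / (79 × 291) = 4.65, p = 0.031.
- Two-way, the 3 also failed: 45 v 31, χ² = 370 × 14² / (76 × 294) = 3.25, p = 0.072.
- Observed-Case: 45 v 21, χ² = 370 × 24² / (66 × 304) = 10.62, p = 0.001.

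| Endpoint | k per arm | Item 5, all placebo changed | Two-way, all changed | Observed-Case |
|---|---|---|---|---|
| ACC | 9 (no trigger) | 48 v 30, 0.022 | 46 v 30, 0.040 | 46 v 21, 0.0007 |
| ACC | 10 | 48 v 31, 0.031 | 45 v 31, 0.072 | 45 v 21, 0.001 |
| ACC | 11 | 48 v 32, 0.043 | 45 v 32, 0.096 | 45 v 21, 0.001 |
| ACC | 12 | 48 v 33, 0.059 | 45 v 33, 0.126 | 45 v 21, 0.001 |
| Pain | 10 | 105 v 76, 0.003 | 99 v 76, 0.017 | 99 v 66, 0.0006 |
| Pain | 13 | 105 v 78, 0.005 | 98 v 78, 0.037 | 98 v 65, 0.0005 |
| Pain | 14 | 105 v 79, 0.007 | 97 v 79, 0.061 | 97 v 65, 0.0008 |
| Pain | 15 | 105 v 79, 0.007 | 96 v 79, 0.077 | 96 v 64, 0.0008 |
| Pain | 24 | 105 v 85, 0.038 | 91 v 85, 0.53 | 91 v 61, 0.0015 |

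For ACC the rules disagree at 10 and 11 per arm; from 12 both tip. For pain neither tips at 10 to 13, and they disagree at every count from 14 to 24, the largest tried.

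**6. Without the equal-split assumption.** At the design rates for ACC, 10 placebo changes give 48 v 32, p = 0.043, so item 5 finds nothing if only 10 imputed placebo Non-responders exist. Failing one imputed APP13007 Responder as well gives 47 v 32, p = 0.057.

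**7. Unequal missingness.** Assume ACC 44 v 22 (p = 0.003), with 10 imputed on APP13007, 6 of them Responders, and 4 imputed placebo Non-responders. Item 5 gives 44 v 26, p = 0.017. Observed-Case gives 38 v 22, p = 0.024. Two-way gives 38 v 26, p = 0.099. Both planned checks stay significant and the combination does not.

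**The case against.** The protocol asks only for a tipping-point analysis and leaves the detail to the SAP, so a one-way version breaks no rule. Each direction is already tested separately. The table in SAP 10.1.2 will show imputed Responders and Non-responders, which are the limits of any two-way grid; a reader could compute the far corner from it.

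That corner is also extreme. In the ACC case with 10 missing per arm, once all 3 imputed APP13007 Responders fail, at least 8 of 9 imputed placebo Non-responders must succeed (45 v 29 gives p = 0.038; 45 v 30 gives 0.052). At the assumed 12% placebo rate, 8 or more of 9 has probability about 3 × 10⁻⁷. The ACC window covers only two counts, and pain needs 14 / 185 = 7.6% missing against a planned 5%. The unequal example depends on 6 of 10 imputed Responders: with 3 of 10 the two-way result is 41 v 26, p = 0.043, still significant.

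Much of this stands. The SAP narrows the protocol's wording but does not contradict it. The counts are assumed, the far corner is a bound rather than a likely outcome, and the unequal example shows only what can happen. None of this supplies the missing analysis. Item 5 itself uses an extreme allocation, but in one arm only, and an arm whose dropout alone starts it is never tested by it. Limits that a reader can reconstruct do not replace a pre-specified result.

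**Conclusion.** The concern holds. Item 5 is one-sided, no other planned analysis combines the two unfavourable directions, and the result can be a report of no tipping point where the same missing data allow one. At the design rates, with equal missing counts split at those rates, this happens for ACC at 10 and 11 missing per arm and for pain from 14 through at least 24 per arm. Observed-Case stays strongly significant at those counts and does not reveal it.

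The missing counts and their split are assumptions. The primary test, alpha and testing order are unaffected. The gap matters only if more than 5% of data are missing in an arm, and it affects the statement of robustness rather than the efficacy claim. It should be corrected because the correction is cheap; it does not undermine the trial.

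**What to change.** Replace item 5 by a two-way tipping grid for each primary endpoint in the ITT population, keeping the trigger and the exclusion of rescued subjects:

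- x = number of imputed, non-rescued APP13007 Responders set to Non-responder, from 0 to all;
- y = number of imputed, non-rescued placebo Non-responders set to Responder, from 0 to all;
- in each cell, the difference in responder rates and the Pearson chi-square p-value, with the p > 0.05 boundary marked.

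The current item 5 is the x = 0 edge, so nothing planned is lost, and the analysis then matches the breadth of Protocol section 10.6. The text should say that the corner with everything changed is a bound, not an expected outcome.

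The cost is one SAP paragraph and a short program loop, with no new data. Stated robustness may look slightly less favourable. The change should be made before unmasking, since a grid added once results are known would carry less weight.

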10.1.4 Additional Analysis

The primary efficacy endpoints will be analyzed using the data collected up to POD15. The rescued subjects will not be considered as treatment failures (Non-responders) for this analysis. All subjects' data collected up to POD15, including the data from subjects who take rescue medication, will be used to analyze the primary efficacy endpoints. Only observed data will be included to derive the primary efficacy endpoints. For the primary endpoint of ACC grade, subjects who miss one of POD 8 and POD15 assessments will be considered as treatment failures (Non-responders). For the primary endpoint of ocular pain grade, subjects who miss one of PODs 4, 8 and 15 assessments will be considered as treatment failures (Non-responders). The Pearson's Chi-square test will be used to test the treatment difference.

10.2 Analyses of Secondary Efficacy Endpoints

10.2.1 Secondary Efficacy Endpoints

The secondary efficacy endpoints are:

- Proportion of subjects with ACC count = 0 (ACC grade = 0) at PODs 4, 8 and 15
- Proportion of subjects with Ocular Pain grade = 0 at PODs 4, 8 and 15
- Proportion of subjects with ACF grade = 0 at POD8 maintained through POD15
- Proportion of subjects with ACF grade = 0 at PODs 4, 8 and 15
- Mean change from baseline in ACC grade at PODs 4, 8, and 15
- Mean change-from baseline in Ocular Pain grade at PODs 4, 8 and 15
- Mean change from baseline in ACF grade on PODs 4, 8 and 15
- Number of subjects rescued on or prior to each visit and overall
- Mean change from baseline in best corrected visual acuity (BCVA) by pinhole method using an ETDRS chart at PODs 4, 8 and 15

The ACC count and Ocular Pain grade will be graded using the same grading scale described for primary efficacy endpoints ([Section 10.1.1](#)).

The ACF will be graded as follow:

Grade	Description
0	None
1	Faint
2	Moderate (iris and lens details clear)
3	Marked (iris and lens details hazy)
4	Intense (fibrin or plastic aqueous)

Subjects who meet the rescue criteria may be rescued and placed on an appropriate alternative therapy as determined by the Investigator. The rescue criteria are provided in the [protocol Section 9.4](#).

The ETDRS visual acuity (logMAR score) will be calculated as follows using Original EDTRS Chart 1 and Chart 2:

1. Determine the last row where the subject can correctly identify at least one (1) letter in that row. This is the base logMAR line.
2. Determine the log score for the base logMAR line.
3. Add 0.02 ($T = 0.02$) log units for every letter that is incorrectly identified up to and including the base logMAR line.

10.2.2 Analysis of Secondary Efficacy Endpoints

10.2.2.1 Analysis of Categorical Endpoints of ACC, Ocular Pain and ACF

The secondary efficacy endpoints (categorical endpoints) of ACC grade, Ocular Pain grade and ACF grade will be analyzed and summarized in the same manner as described for the primary efficacy endpoints ([Section 10.1.2](#)). The imputation for missing values for the categorical endpoints is described in [Section 6.4.3.1](#). The proportion of subjects with ACC grade = 0, Ocular Pain grade = 0, and ACF grade = 0 at PODs 4, 8, and 15 will be plotted separately for each of these endpoints.

In addition, the ACC grade, Ocular Pain grade and ACF grade will be tabulated, including the number and percentage of subjects in each grade category, using the observed data only.

10.2.2.2 Analysis of Continuous Endpoints of ACC, Ocular Pain, ACF and BCVA

Mean change from baseline in ACC grade, Ocular Pain grade, ACF grade and BCVA at PODs 4, 8 and 15 will be analyzed using an analysis of covariance (ANCOVA). The ANCOVA model will include treatment as a fixed effect and baseline as a covariate. The imputation for missing values for the continuous endpoints is described in [Section 6.4.3.1](#).

The values of the endpoints and change from baseline at PODs 4, 8 and 15 will be summarized by treatment group using descriptive statistics, including 95% CI for the mean of the change-from-baseline. The adjusted mean of the change from baseline and the treatment difference of adjusted means with associated 95% CI from ANCOVA will be presented. The mean change from baseline with 95% CI at PODs 4, 8 and 15 will be plotted.

In addition, the ACC grade, Ocular Pain grade, ACF grade and BCVA, and change from baseline will be summarized descriptively using the observed data only.

10.2.2.3 Analysis of Endpoint of Rescue Medication Use

The overall number of subjects rescued during the treatment period will be compared between treatment groups using the Pearson Chi-square test. “Rescued during treatment period” is defined as use of rescue medications during the 14-day study drug treatment period. When the treatment duration of study drug is < 14 days, use of rescue medications will be excluded from the analysis when rescue medications are started > 2 days after the last dose of study drug.

In addition, the cumulative number of subjects rescued at PODs 4, 8, and 15 will be summarized by treatment group and compared between treatment groups using the Pearson Chi-square test at each Analysis Visit. In addition, the number and percentage of subjects rescued in each category of criteria for rescue will be presented for the overall study and at PODs 4, 8, and 15. If multiple rescue medications are used by a subject, only the first time a rescue medication is used will be included in the analysis and summary.

11. SAFETY ANALYSES

The extent of exposure and all safety endpoints will be summarized using the Safety population. For all safety endpoints, the observed data and scheduled visits will be used for summary statistics. No imputation of missing data will be employed.

